Figure 2. Semi-quantitative (grade 0-3) grey-scale ultrasound synovitis score at the wrist joint in the dorsomedian longitudinal axis

[figure not shown]

Figure 1 Semi-quantitative (grade 0-3) grey-scale ultrasound synovitis score at the wrist joint in the dorsomedian longitudinal axis.

Figure 3. Semiquantitative (grade 0-3) grey-scale ultrasound synovitis score at the metacarpophalangeal II/III joints in the palmar longitudinal axis

[figure not shown]

Figure 3 Semiquantitative (grade 0-3) grey-scale ultrasound synovitis score at the metacarpophalangeal II/III joints in the palmar longitudinal axis.

The PDUS evaluation for synovitis (see Figure 4 and Figure 5) and tenosynovitis/paratenonitis is scored according to the scoring system of Szkudlarek et al. (2003).

Tenosynovitis/paratenonitis and erosions in GSUS are registered on a binary basis (0/1).

Figure 4. Semiquantitative (grade 0-3) power Doppler ultrasonography synovitis score at the wrist joint in the dorsomedian longitudinal axis

[figure not shown]

Figure 2 Semiquantitative (grade 0-3) power Doppler ultrasonography synovitis score at the wrist joint in the dorsomedian longitudinal axis.

Figure 5. Semiquantitative (grade 0-3) power Doppler ultrasonography synovitis score at the metacarpophalangeal II/III joints in the dorsal longitudinal axis

[figure not shown]

Figure 4 Semiquantitative (grade 0-3) power Doppler ultrasonography synovitis score at the metacarpophalangeal II/III joints in the dorsal longitudinal axis.

A recently published US7 reliability study investigated the inter-observer and intra-observer reliability of sonographers, determining the US7 score under conditions similar to those of daily rheumatological practice. The median overall κ value for detecting synovitis was $\kappa=0.51$, for tenosynovitis/paratenonitis $\kappa=0.57$ and for erosions $\kappa=0.45$. This study also showed that the US7 score has the potential also in multicentre analysis to assess structural changes with moderate to good reliability (Ohrndorf et al. 2012).

In today's clinical practice, there is still an existing need to define which remission criterion can best be used to predict remission in the long run.

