6. RESEARCH QUESTION AND OBJECTIVES

This study aims both to evaluate remission according to different criteria and to look at which remission criterion at Month 6 is the most predictive for remission at Month 12.

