6.1. Primary Objective

To determine which remission criterion at Month 6 predicts remission at Month 12 the best.

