6.2. Secondary Objectives

- Describe the percentage of patients in remission at the different DCPs (Data Collection Points) according to different remission criteria: CDAI, SDAI, DAS28, DAS28 in combination with Ultrasound, EULAR Boolean definition for clinical practice and clinical studies.
- Describe percentage of the same patients in remission at the different DCPs, according to different remission criteria: CDAI, SDAI, DAS28, DAS28 in combination with Ultrasound, EULAR Boolean definition for clinical practice and clinical studies.
- Determine if the quantitative change in between baseline and Month 6 is predictive for the change at Month 12.
- Determine which single component is the most predictive for the composite index of remission.
- Determine predictors for remission, according to all the different criteria at each timepoint.
- Comparison between DAS28 remission and US remission

- Prediction of remission based on US data

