7. RESEARCH METHODS

7.1. Study design

This will be an observational, multicenter study, in which patients with RA will be recruited in 2 cohorts. The study design can be found in Figure 6.

The first cohort is a cohort in which the decision by the treating rheumatologist has been taken to start treatment with Enbrel as first biological product, according to prevailing reimbursement criteria in Belgium and dosing in line with the Summary of Product Characteristics (SmPC).

The second cohort is a cohort in which the decision of the treating rheumatologist has been taken to start treatment with Enbrel according to prevailing reimbursement criteria in Belgium as second biological product (either after use of another anti-TNF or another mechanism of action) and dosing in line with SmPC.

The study flow chart can be found in Table 1.

At baseline, demographics, disease duration (defined as the time between diagnosis and etanercept treatment initiation), Health Assessment Questionnaire (HAQ) and different remission criteria (DAS28, SDAI, CDAI, Boolean definition of both CDAI and SDAI, DAS28 in combination with US) will be recorded.

The evaluation will take place at Data Collection Points (DCPs) which will coincide with regular visits, not scheduled for the purpose of the study, but at Q3 months with a time window of \pm one month, recording the same data, as well as current medication and related adverse events (AEs).

The ultrasound will only take place in selected centers with a proven record of US training and day-to-day clinical experience. Bruyn et al. (2013) concluded that the scoring of US intra-reader variability was excellent ($\kappa=0.91$) and inter-reader variability was good ($\kappa=0.75$).

A recently published US7 reliability study investigated the inter-observer and intra-observer reliability of sonographers, determining the US7 score under conditions similar to those of daily rheumatological practice. The median overall κ value for detecting synovitis was $\kappa=0.51$, for tenosynovitis/paratenonitis $\kappa=0.57$ and for erosions $\kappa=0.45$. This study also showed that the US7 score has the potential also in multicentre analysis to assess structural changes with moderate to good reliability (Ohrndorf et al. 2012).

Ultrasound images will be collected and saved. When needed for analysis, they can afterwards be read by central readers.

Figure 6. Study design

[figure not shown]

Table 1. Study flow chart

	Baseline	DCP1	DCP 2	DCP 3	DCP 4

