Time	0 m	Month 3 (2-4)	Month 6 (5-7)	Month 9 (8-10)	Month 12 (11-13)
Demographics	X				
Disease duration	X				
DAS28	X	X	X	X	X
SDAI	X	X	X	X	X
CDAI	X	X	X	X	X
BOOLEAN CDAI SJC≤1, TJC≤1, PtGA≤1	X	X	X	X	X
BOOLEAN SDAI SJC≤1, TJC≤1, PtGA≤1 and CRP≤1	X	X	X	X	X
Ultrasound (Selected Centers)	X		X		X
HAQ	X	X	X	X	X
Current medication	X	X	X	X	X
Adverse events	X	X	X	X	X

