7.3. Variables

Table 2. Variables, roles, data sources and operational definitions

Variable	Role	Data source(s)	Operational definition
Demographics	Baseline variables	Medical records	Please refer to the SAP*
Disease duration	Baseline variables	Medical records	Please refer to the SAP*
Cohort 1 or 2	Sub-group identifier	Medical records	Please refer to the SAP*
DAS28	Outcome variable	Medical records	Please refer to the SAP*
SDAI	Outcome variable	Medical records	Please refer to the SAP*
CDAI	Outcome variable	Medical records	Please refer to the SAP*
BOOLEAN CDAI SJC \leq 1, TJC \leq 1, PtGA \leq 1	Outcome variable	Medical records	Please refer to the SAP*
BOOLEAN SDAI SJC \leq 1, TJC \leq 1, PtGA \leq 1 and CRP \leq 1	Outcome variable	Medical records	Please refer to the SAP*

Variable	Role	Data source(s)	Operational definition
Ultrasound (Selected Centers)	Outcome variable	Medical records	Please refer to the SAP*
HAQ	Outcome variable	Medical records	Please refer to the SAP*
Current medication	Exposure	Medical records	Please refer to the SAP*
Adverse events	Safety	Medical records	Please refer to the SAP*

* SAP = Statistical Analysis Plan

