7.7. Data analysis

Detailed methodology for summary and statistical analyses of data collected in this study will be documented in a SAP, which will be dated, filed and maintained by the sponsor. The SAP may modify the plans outlined in the protocol; any major modifications of primary endpoint definitions or their analyses would be reflected in a protocol amendment.

The analysis of the primary endpoint will be based on a logistic regression defining the dependent variable as the remission at month 12 and the 5 independent variables as CDAI, SDAI, DAS28, DAS28 and Ultrasound, and EULAR Boolean definition for clinical practice and clinical studies. This analysis will be conducted in each arm of the study as well as after a pooling of both patient groups.

The other statistical methods used for the analysis of the data will be mainly descriptive.

Appropriate inferential analyses will be used to compare the over-time modifications of study parameters and potentially to compare the two arms of the study.

Time to event variables will be analyzed using the Kaplan-Meier's method with comparison between groups being ensured by the log rank test.

An interim analysis of baseline data will be performed at Month 6.

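### As most naturally read, the primary model enters five overlapping Month 6 criteria together, so it estimates what each adds to the others, whereas the objective asks which one predicts best.

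*Combined protocol and SAP*

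**What the plan says.** Section 5 of the protocol gives the motivation: "there is still an existing need to define which remission criterion can best be used to predict remission in the long run". Section 6 asks "which remission criterion at Month 6 is the most predictive for remission at Month 12", and section 6.1 makes that the sole primary objective: "To determine which remission criterion at Month 6 predicts remission at Month 12 the best". All three ask for a ranking of individual criteria.

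Sections 7.5 and 7.7 describe the primary analysis in nearly the same words: a "logistic regression defining the dependent variable as the remission at month 12 and the 5 independent variables as CDAI, SDAI, DAS28, DAS28 and Ultrasound", followed by the EULAR Boolean definition for practice and for studies. Sections 3 and 7.5 refer to a single predictive model. Section 7.7 plans the analysis in each arm and pooled; section 7.5 makes the per-arm runs conditional on feasibility.

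Section 6.2 and Table 1 list six criteria. Table 1 has one Boolean on swollen joints, tender joints and patient global assessment, and a second that adds CRP: "BOOLEAN SDAI SJC≤1, TJC≤1, PtGA≤1 and CRP≤1". Ultrasound is not universal: "The ultrasound will only take place in selected centers with a proven record of US training and day-to-day clinical experience". For operational definitions Table 2 says "Please refer to the SAP". No separate SAP text is in the supplied document.

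**The concern.** A rheumatologist choosing one criterion at Month 6 needs to know how well each predicts when used alone. A joint logistic model answers a different question: how much a criterion still tells you when the other four are already known.

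The two answers diverge most when predictors share content, and here they do. DAS28 enters alone and again combined with ultrasound, CDAI and SDAI are closely related, and the two Booleans differ only by CRP. A small joint coefficient for DAS28 with ultrasound could be reported as poor prediction although the model never tested that criterion alone. Joint estimates are also less stable than single-criterion estimates at the planned size of about 100 completers, with fewer in any model that needs ultrasound.

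**Working it through.** **The plan's own figure.** The only size calculation that can be reproduced is recruitment per arm. With 30% drop-out, 50 / (1 - 0.30) = 71.4, against the stated 70; 70 x 0.70 = 49 completers, consistent with about 50. The point does not depend on it. Section 7.5 says the sample size has no inferential justification, so there is no power figure to check.

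**What each model estimates.** Let Y be Month 12 remission and X1 to X5 the Month 6 criteria.

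- Joint model: logit P(Y=1) = b0 + b1X1 + ... + b5X5. Each b compares patients who differ on that criterion but agree on the other four.
- Single models: logit P(Y=1) = aj + gjXj, one per criterion. Each g compares patients who meet criterion j with those who do not, which is the comparison the objective needs.

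Suppose DAS28 with ultrasound means that both conditions are met (an assumption; the supplied text gives no rule). With DAS28 also in the model, the coefficient of the combined criterion is then only the contrast between ultrasound remission and no ultrasound remission among patients already in DAS28 remission, given the remaining criteria. It does not show how well the combined criterion predicts.

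**Illustration.** All inputs are assumptions.

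- Criteria: correlated normal variables at Months 6 and 12, cut to yes/no.
- Base correlations: 0.8 between clinical indices, 0.95 between CDAI and SDAI, 0.4 between ultrasound and the clinical indices. Cross-time correlations are 0.6 times these.
- Base remission rates: CDAI 22%, SDAI 22%, DAS28 40%, Boolean 18%, ultrasound 50%.
- Nine further settings vary correlations, rates and persistence. With five possible Month 12 definitions this gives 10 x 5 = 50 combinations.
- AUC of a yes/no criterion = (sensitivity + specificity) / 2.

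Base setting, DAS28 as the Month 12 definition, 400,000 simulated patients:

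| Month 6 criterion | AUC alone | log OR alone | log OR jointly |
|---|---|---|---|
| CDAI | 0.621 | 1.41 | 0.22 |
| SDAI | 0.622 | 1.43 | 0.28 |
| DAS28 | 0.702 | 1.74 | 1.36 |
| DAS28 + ultrasound | 0.641 | 1.46 | 0.07 |
| Boolean | 0.608 | 1.47 | 0.39 |

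DAS28 with ultrasound is second by AUC alone and last jointly; its odds ratio falls from exp(1.46) = 4.3 to exp(0.07) = 1.07. The Boolean goes the other way, from last by AUC to second jointly. DAS28 is first on every column.

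Across the 50 combinations, the largest joint coefficient and the best separate AUC named the same top criterion in 48, and a different second-placed criterion in 32. DAS28 with ultrasound came last jointly in 43 and last by AUC alone in 12.

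**At 100 patients** (2,000 simulated studies per combination; 1,000 for separate-fit failures):

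- The ratio of the median joint to the median single-criterion standard error ran from 1.31 to 2.00 over criteria and combinations.
- In the base setting the joint fit was unusable through separation in about 5-9% of runs, against under 1% in which any separate fit was unusable.

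A fresh run of the base setting agreed with the table to within about 0.02 and with these failure rates.

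**Per-arm runs.** The amendment lets patients enter either cohort, after 34 had joined the first and 4 the second. If that split continued, 4/38 = 10.5% of 100 completers, about 11 patients, would be in the second cohort. The final split is not given.

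**The case against.** **Separate models may be intended.** The text never says the criteria are entered simultaneously. The singular wording favours one model but does not exclude five. If five are meant, one sentence settles it, though the comparison measure would still need stating.

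**The SAP may settle it.** This stands for the details. Which definition is the Month 12 outcome, how DAS28 and ultrasound combine, whether criteria enter as scores or yes/no, and whether there are five or six are deferred to a SAP that was not supplied. A reader might infer that the plan lacks them; the documents do not support that. The mismatch between sections 6.1 and 7.7 is within the protocol itself, and 7.7 says that major changes to the primary analysis would be reflected in an amendment.

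**The winner hardly changes.** This also stands. A reader might infer that the joint model will name the wrong criterion. The large-sample agreement in 48 of 50 combinations argues against that.

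**Separate fitting is not always better at finding the winner.** For the DAS28 outcome at 100 patients (base setting), the separate AUC named the best criterion in 88% of runs and the largest joint coefficient in 52%. It is tempting to credit that gap to separate fitting. However, it changes the measure as well as the model: ranked by separate odds ratios, the best criterion was found in only about 44%. For the other four outcomes separate odds ratios led the joint model, by about 4-16 points. Any gain depends on the measure, and 52 against 88% does not measure the effect of separate fitting.

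**Ultrasound is examined elsewhere.** Section 6.2 includes "Determine predictors for remission, according to all the different criteria at each timepoint", a comparison of DAS28 with ultrasound remission, and prediction from ultrasound data. These partly offset the risk but are secondary, and no model is given for them.

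**Conclusion.** The mismatch holds on the natural reading of sections 7.5 and 7.7: the objective asks for stand-alone prediction and the primary model estimates added value. This follows from the text and from what a joint coefficient means, whatever the simulation inputs.

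The sizes do depend on assumed rates, correlations and yes/no coding. In particular, the separation rates would not carry over if continuous scores were entered. Within those limits the consequences are a possible misreading of DAS28 with ultrasound, standard errors about 1.3 to 2 times larger, and a modest rate of failed fits at 100 patients. A systematically wrong winner is not shown.

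Per-arm runs are at least as fragile as the pooled one, but no failure rate should be attached to them. Balanced arms of 50 are no longer planned, and a six-variable model is not what the plan states.

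This should be fixed, with medium confidence, because separate models remain a possible intention and the SAP was not available.

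**What to change.** In sections 7.5 and 7.7, or in the SAP with a protocol amendment if it counts as a major modification:

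1. Make the primary analysis one logistic model per Month 6 criterion, all fitted on the same patients (those with ultrasound). Repeat the non-ultrasound criteria in all completers.
2. Compare criteria by one measure stated in advance, for example AUC, with paired confidence intervals for the differences.
3. Name one Month 12 remission definition as the primary outcome before Month 12 results are seen.
4. Keep the joint model as a secondary analysis, labelled as added value.
5. Carry the feasibility condition on per-arm runs from 7.5 into 7.7.
6. Confirm in the SAP the DAS28-ultrasound rule, the coding of the criteria, and whether the two Booleans count as one or two.

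The cost is wording, a few more tables and possibly an amendment; no new patients or data are needed. Two limits remain. The choice of measure can affect the ranking (separate odds ratios and AUC named different winners in 16 of the 50 combinations), so it must be fixed in advance. About 100 patients, fewer with ultrasound, may still not separate criteria that predict almost equally well.

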7.8. Quality control

The sponsor will perform quality control and assurance checks of the study. Before enrolling any subjects in this study, sponsor personnel and the investigator will review the protocol, the SmPC, the eCRF and the instructions for their completion, the procedure for obtaining informed consent, and the procedure for reporting AEs and serious adverse events (SAEs).

A qualified representative of the sponsor will monitor the conduct of the study by visiting the site and by contacting the site by telephone. During the visits, information recorded on the eCRFs will be verified against source documents. Automatic inconsistencies will be generated by the ePlatform directly in the eCRF and Clinical Research Associates will have the opportunity to add manual queries directly in the eCRF.

All statistical programs used to manage and analyze the data will be validated and archived with the clinical database.

7.9. Limitations of the research methods

The limitations of the study are intrinsic to its observational, non-controlled, non-randomized design.

7.10. Other aspects

Not applicable.

8. PROTECTION OF HUMAN SUBJECTS

8.1. Patient Information and Consent

All parties will ensure protection of patient personal data and will not include patient names on any sponsor forms, reports, publications, or in any other disclosures, except where required by laws. In case of data transfer, Pfizer will maintain high standards of confidentiality and protection of patient personal data.

The informed consent form must be in compliance with local regulatory requirements and legal requirements.

The informed consent form used in this study, and any changes made during the course of the study, must be prospectively approved by both the Institutional Review Board (IRB), the Independent Ethics Committee (IEC) and Pfizer before use.

The investigator must ensure that each study patient, or his/her legally acceptable representative, is fully informed about the nature and objectives of the study and possible risks associated with participation. The investigator, or a person designated by the investigator, will obtain written informed consent from each patient or the patient's legally acceptable representative before any study-specific activity is performed. The investigator will retain the original of each patient's signed consent form.

8.2. Patient withdrawal

Patients may withdraw from the study at any time at their own request, or they may be withdrawn at any time at the discretion of the investigator or sponsor for safety, behavioral, or administrative reasons. In any circumstance, every effort should be made to document subject outcome, if possible. The investigator should inquire about the reason for withdrawal and follow-up with the subject regarding any unresolved adverse events.

If the patient withdraws from the study, and also withdraws consent for disclosure of future information, no further evaluations should be performed, and no additional data should be collected. The sponsor may retain and continue to use any data collected before such withdrawal of consent.

8.3. Institutional Review Board (IRB)/Independent Ethics Committee (IEC)

It is the responsibility of the investigator to have prospective approval of the study protocol, protocol amendments, and informed consent forms, and other relevant documents, (e.g., recruitment advertisements), if applicable, from the IRB/IEC. All correspondence with the IRB/IEC should be retained in the Investigator File. Copies of IRB/IEC approvals should be forwarded to Pfizer.

8.4. Ethical Conduct of the Study

The study will be conducted in accordance with legal and regulatory requirements, as well as with scientific purpose, value and rigor and follow generally accepted research practices described in *Guidelines for Good Pharmacoepidemiology Practices* issued by the International Society for Pharmacoepidemiology, Good Epidemiological Practice guidelines issued by the International Epidemiological Association, Good Practices for Outcomes Research issued by the International Society for Pharmacoeconomics and Outcomes Research, International Ethical Guidelines for Epidemiological Research issued by the Council for International Organizations of Medical Sciences, European Medicines Agency, European Network of Centres for Pharmacoepidemiology and Pharmacovigilance, Guide on Methodological Standards in Pharmacoepidemiology.

9. MANAGEMENT AND REPORTING OF ADVERSE EVENTS/ADVERSE REACTIONS

9.1. Requirements

Table 3 below summarizes the requirements for recording safety events on the eCRF and for reporting safety events on the non-interventional study (NIS) adverse event monitoring (AEM) Report Form to Pfizer Safety. These requirements are delineated for three types of events: (1) SAEs; (2) non-serious AEs (as applicable); and (3) scenarios involving drug exposure, including exposure during pregnancy (EDP), exposure during breast feeding, medication error, overdose, misuse, extravasation, and occupational exposure. These events are defined in the section “Definitions of safety events”.

Table 3. Requirements for recording and reporting safety events

Safety event	Recorded on the eCRF	Reported on the NIS AEM Report Form to Pfizer Safety within 24 hours of awareness
SAE	All	All
Non-serious AE	All	None: Even if the study involves a site of the European Economic Area (EEA), the study team decided that the non-serious adverse events should not be reported to Pfizer Safety because none of the objectives of the study involves the active collection of safety information and the clinical team doesn't want to actively seek any specific non-serious adverse events.
Scenarios involving exposure to a drug under study, including EDP, exposure during breast feeding, medication error, overdose, misuse, extravasation; lack of efficacy; and occupational exposure	All (regardless of whether associated with an AE), except occupational exposure	All (regardless of whether associated with an AE)

For each AE, the investigator must pursue and obtain information adequate both to determine the outcome of the adverse event and to assess whether it meets the criteria for classification as a SAE (see section "Serious Adverse Events" below).

Safety events listed in the table above must be reported to Pfizer within 24 hours of awareness of the event by the investigator **regardless of whether the event is determined by the investigator to be related to a drug under study**. In particular, if the SAE is fatal or life-threatening, notification to Pfizer must be made immediately, irrespective of the extent of available event information. This timeframe also applies to additional new (follow-up)

information on previously forwarded safety event reports. In the rare situation that the investigator does not become immediately aware of the occurrence of a safety event, the investigator must report the event within 24 hours after learning of it and document the time of his/her first awareness of the events.

For safety events that are considered serious or that are identified in the far right column of the table above that are reportable to Pfizer within 24 hours of awareness, the investigator is obligated to pursue and to provide any additional information to Pfizer in accordance with this 24-hour timeframe. In addition, an investigator may be requested by Pfizer to obtain specific follow-up information in an expedited fashion. This information is more detailed than that recorded on the eCRF. In general, this will include a description of the adverse event in sufficient detail to allow for a complete medical assessment of the case and independent determination of possible causality. Any information relevant to the event, such as concomitant medications and illnesses must be provided. In the case of a patient death, a summary of available autopsy findings must be submitted as soon as possible to Pfizer or its designated representative.

